#### The Paper Fax-to-Quit Tobacco Quitline Referral System

A paper *Fax-to-Quit (F2Q)* program for the Wisconsin Tobacco Quit Line (WTQL) was developed in 2003 by UW-CTRI as a mechanism to provide evidence-based tobacco cessation treatment to clinic and hospital patients. This system was developed in response to health system requests to more efficiently link their patients to the WTQL (see Figure 1 for F2Q workflow description). Once a healthcare system requests implementation of a F2Q program, UW-CTRI Outreach staff travel to the clinic or hospital to train staff on using the program and provide necessary materials (e.g., clinic-specific F2Q referral form – Figure 2). Utilizing F2Q is relatively simple but requires a number of steps. First, staff have to query patients regarding their tobacco use status. Staff then describe WTQL services (tobacco cessation counseling and nicotine replacement therapy) to the identified tobacco user and ask if the patient is interested in receiving such services. If the patient agrees and provides written permission, staff then manually complete a paper F2Q form that includes contact information and best times for the WTQL to call the patient. The form is then manually faxed by a clinic staff person to the WTQL; the WTQL then attempts to contact the patient within 48 hours and deliver WTQL treatment services. Depending on the clinic, different staff members assume responsibility for these different tasks. Finally, the WTQL faxes back to the referring clinic/provider (not to the patient's chart) a form describing the outcome of the referral, including whether their patient was reached, if s/he agreed to receive services, and which services were provided. Clinics are encouraged to enter such QL treatment information into the patient's EHR (via scanning or manually), but few clinics report doing so. Since 2003, approximately 1,000 healthcare settings (clinics, hospitals) in Wisconsin have implemented a F2Q program, with 221 active (referred at least one patient to the WTQL) in 2014 (many clinics that implement F2Q don't continue to use it, in part due to the cumbersome operational requirements). In 2014, these 221 active sites referred a total of 2,420 patients to the WTQL, averaging 11 referrals per clinic per year (WTQL data). Of the patients fax referred, 41% enrolled in WTQL services.

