The analysis of the primary outcome is designed to show differences in the rate at which patients are referred to the Wisconsin Tobacco Quitline by the 12 control (F2Q) versus the 12 experimental (EHR referral) clinics during the post-intervention period. We will use a mixed effects logistic regression model via Generalized Estimating Equations (via SAS PROC GENMOD; for a population based model) with coding for the baseline and post-intervention phases, and with coding for each post-intervention monthly time point with the models centered at the 6-month post-intervention mark. Based on data from the healthcare systems, we anticipate that on average, each clinic will see about 120 smokers/month, and based upon the urn randomization procedure we expect similar smoker flow rates across the two experimental conditions. The binary dependent variable will be measured at the smoker level, i.e., whether or not a smoker seen at a clinic is referred to the quitline, and aggregated to the clinic level to constitute clinic referral rate. Thus, while clinic is the unit of analysis, our sample is the smoker, each one being one Level 1 unit. Experimental condition will be coded with a single dummy variable. The baseline WTQL referral rate data for each clinic will serve as a covariate (only one covariate will be used to preserve degrees of freedom). We will specify a logit link function and assume a first-order autoregressive structure (to address dependence across measurement occasions). We will test the main effects of experimental conditions. Further, we have an a priori plan to test for post-intervention change over time within each experimental condition and will test for interaction between experimental condition and measurement occasion. Similar analyses will be used for the quality referral outcome.

In a subsequent model we will analyze cessation rates of tobacco patients identified as smokers during a clinic visit. Abstinence will be measured at the smoker level and aggregated to the clinic level by the WTQL to determine a clinic quit rate. We anticipate that there will be no overlap in rates of abstainers/clinic (abstainers from a clinic/smokers presenting to clinics within the relevant time period) for the two experimental conditions, permitting use of a non-parametric analysis of outcome (e.g., Mann-Whitney U).

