2/28/2017 Amendment. Given that the objective of the SmokefreeTXT eReferral pilot study is to assess the feasibility, uptake, retention, and quit rates of this program, there are no specific quantitative hypotheses to test or comparisons to be conducted. Instead, analyses will be descriptive and will focus on uptake, retention, and quit rates by clinic. We will also assess staff knowledge of smoking cessation treatments and SmokefreeTXT-specific knowledge, practices, and attitudes prior to and after six months of SmokefreeTXT eReferral, with the expectation that knowledge, positive attitudes, and treatment practices among clinic personnel will improve from pre- to post-launch. In addition, we will document implementation challenges and solutions to inform future evaluation or dissemination efforts.

**Power Analyses for Intervention Phase:** Power was calculated for a two-group cluster-randomized design with clinic as the unit of randomization (n=6 clinics per group for each health system) with a conservative estimate of approximately 90 smokers seen in each clinic per month. The dependent variable for the power analysis is the proportion of smokers referred/month. We based our estimates of

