the mean number of monthly referrals in each group on pilot data from an eReferral demonstration project (Adsit et al., 2014) which found a rate of 14% for an eReferral system versus 0.3% for a paper fax referral system^4. To achieve a more conservative power analysis, we calculated power to detect a smaller difference between the groups. More specifically, we estimated power to detect a group difference on proportion referred per month with values of 2% for the Fax to Quit group versus 7% for the eReferral group. As shown in Table 3, the groups are not expected to differ at baseline (mean of 1% referrals per month for each group). As such, the power analysis was based on a test of the difference between groups for the post-intervention proportion of referrals per month (2 vs 7%). The following power analysis therefore should be conservative since it does not take advantage of baseline referral rate to index change and its projected effect size is considerably less than might be expected based on prior research. For purposes of power analysis, we assumed that the standard deviation for the mean proportion of referrals per month will be 2.5%; we also set alpha at .05 for a two-tailed test. The power analysis was computed via an online program, GLIMMMPSE, that permits power estimation for cluster-randomized designs. Results of the power analysis showed that there is >90% power to detect a mean difference of 1 versus 7% of smokers referred per month. The demonstration of this effect within two health systems will allow even greater confidence in these primary outcomes.

**Table 3. Predicted Mean Rates of Quitline Contacts/Clinic/Month as Proportions of Smokers Seen, Two Arms Across Baseline and Intervention Phases**

Intervention Arm	Baseline	Intervention
Fax Referral (Fax to Quit)	1%	2%
EHR-based Referral (eReferral)	1%	7%

2/28/2017 Amendment. Formal power analyses were not conducted for the pilot test of the feasibility of eReferral to SmokefreeTXT that will be conducted in 1-3 clinics.

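### The cessation test is justified by an expected absence of overlap between arms, which Mann-Whitney does not need and the planning values make unlikely; the test named also ignores the health-system strata

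*Combined protocol and SAP*

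**What the plan says.** The section Hypotheses & Analytic Plan for Intervention Phase aggregates abstinence to a quit rate per clinic, defined as abstainers over smokers presenting. It then states "We anticipate that there will be no overlap in rates of abstainers/clinic" for the two conditions, "permitting use of a non-parametric analysis of outcome (e.g., Mann-Whitney U"). The test is an example, and no other analysis is named for the case where clinics overlap.

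The documents give no quit rate, follow-up response rate, expected abstainer count or power for cessation. The only power figure concerns referral. It rests on "values of 2% for the Fax to Quit group versus 7% for the eReferral group" and on the assumption that "the standard deviation for the mean proportion of referrals per month will be 2.5" per cent.

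Under Clinic Randomization, clinics are stratified by health system and allocated six to each condition within each system. The cessation paragraph does not mention the strata.

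**The concern.** Two things are wrong with the reasoning. First, a rank test does not depend on the arms being separated; it is valid with any amount of overlap. Second, the plan makes a method follow from an expected result. Complete separation of 12 v 12 clinics would give an exact two-sided p of 2/C(24,12) = 2/2,704,156 = 7 x 10^-7. The sentence therefore treats a decisive cessation finding as the expected one, without a count to support it.

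If the clinics do overlap, the stated ground for the test is gone, and because the test is only an example, the choice is open after the data are seen. That matters for Secondary Aim 2 and for the third listed hypothesis, which both concern cessation.

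**Working it through.** **The plan's own figure first.** The stated power for referral is above 90%. With 2% v 7%, SD 2.5 points and "we also set alpha at .05 for a two-tailed test", power is Φ(0.05 / (0.025 x √(2/n)) − 1.96) for n clinics per arm.
- n = 12: Φ(4.90 − 1.96) = 0.998.
- n = 6 (one system): Φ(3.46 − 1.96) = 0.934.

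The figure reproduces. It says nothing about cessation.

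**Inputs for cessation**
- Smokers per clinic per month: 120 in the analytic plan ("each clinic will see about 120 smokers/month"); 90 in the power section ("a conservative estimate of approximately 90 smokers seen in each clinic per month").
- Referral: 2% v 7%.
- Enrolment: "Of the patients fax referred, 41% enrolled in WTQL services". This is a fax figure, and its use for both arms is an assumption.
- Window: six months of referral monitoring (Study Implementation Phase); 12 months as an alternative.
- Quit rate among enrollees: not given; assumed 10-40%, with complete follow-up.

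**Enrollees per clinic, six months** = smokers/month x 6 x referral rate x 0.41
- Fax: 90 x 6 x 0.02 x 0.41 = 4.4; 120 x 6 x 0.02 x 0.41 = 5.9.
- eReferral: 90 x 6 x 0.07 x 0.41 = 15.5; 120 x 6 x 0.07 x 0.41 = 20.7.

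**Abstainers per clinic** = enrollees x quit rate
- Fax: 4.4 x 0.10 = 0.4 to 5.9 x 0.40 = 2.4.
- eReferral: 15.5 x 0.10 = 1.6 to 20.7 x 0.40 = 8.3.

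**Chance of no overlap**, that is, every eReferral clinic above every fax clinic. One case can be done by hand: 120/month, six months, 20% quitting, identical clinics, Poisson means 1.18 and 4.13. Sum over k the probability that the highest fax count equals k times the probability that all 12 eReferral counts exceed k.
- k = 1: 0.670^12 = 0.008; 0.918^12 = 0.357; product 0.003.
- k = 2: 0.884^12 − 0.008 = 0.218; 0.781^12 = 0.051; product 0.011.
- k = 3: 0.968^12 − 0.227 = 0.449; 0.592^12 = 0.0019; product 0.001.
- Total: about 0.015, or 1.5%.

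Simulation (20,000 runs, beta-binomial counts, equal clinic volumes) gives, at 120 smokers/month:

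| Referral rates, window | Quit rate | Identical clinics | Between-clinic SD 2.5 points |
|---|---|---|---|
| 2% v 7%, 6 months | 20% | 1.5% | 0.5% |
| 2% v 7%, 6 months | 30% | 6.9% | 1.2% |
| 2% v 7%, 12 months | 30% | 46% | 3% |

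Over six months at quit rates of 10-30%, with the 2.5-point SD in the eReferral arm, the range is 0.0-2.1%. The most favourable six-month case (40% quitting, 120/month, identical clinics) reaches 18%. At the pilot's 14% v 0.3%, with 20-30% quitting, it is 76-99.8%.

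The plan's 2.5% is the SD of a monthly proportion. Binomial noise alone at 7% is √(0.07 x 0.93/120) = 2.3 to √(0.07 x 0.93/90) = 2.7 points, so true between-clinic spread may be smaller. Both ends, 0 and 2.5, are therefore shown.

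**Does the rank test lose power?** At 120/month, six months, 20% quitting and SD 2.5 points in both arms, power is 0.92 for Mann-Whitney, 0.87 for the t-test, 0.92 for the t-test on square-root counts and 0.82 for quasi-Poisson. With identical clinics, or SD proportional to the mean, Mann-Whitney is 0-4 points below the t-test. With 2% in both arms and SD 2.5 points, its type I error is 0.044-0.047. A pooled exact test that ignores clinics has more power but a type I error of 0.20-0.42 there.

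**Stratifying by health system.** Keeping the rank-sum statistic and re-allocating clinics six:six within system costs at most about 1 point of power if the systems do not differ. It gains 0-3 points if they differ by ±0.2 on the log rate (a ratio of e^0.4 = 1.5), and 4-8 points at ±0.5 (e^1.0 = 2.7). The system effects are assumed.

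**The case against.** The best defence is that the power section calls 2% v 7% deliberately conservative and reports pilot rates of 14% v 0.3%. At those rates, separation of the arms is plausible, and over 12 months with identical clinics it is not rare even at 2% v 7%. That stands: the expectation is not absurd. But Table 3 gives 2% and 7% as the predicted rates, and the sentence in question states no rates or window of its own.

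A reader might infer three stronger points that the documents do not support.

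- That the rank test wastes power. It does not in general. Against a permutation test on pooled abstainers/smokers, with equal clinics and SD 2.5 points, Mann-Whitney is ahead by 5-9 points (for example 89 v 83% at 90/month and 20% quitting). The pooled test gains clearly only when clinic sizes are made unequal (assumed coefficient of variation 0.6) and clinic rates have a coefficient of variation of 0.5: 77 v 66% in one such case, but 74 v 73% with SD 2.5 points. It also weights clinics by volume, whereas Secondary Aim 2 asks for per-clinic rates.
- That the plan's figures alone yield a handful of abstainers. They yield enrollees; the quit rate is an assumption.
- That overlap is nearly certain whatever happens. This depends on window, spread and referral rates, as shown above.

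It is also fair that the sentence sets no rule for switching tests and that cessation is a secondary aim.

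**Conclusion.** The justification fails; the test does not. Mann-Whitney needs no separation of the arms. At the plan's planning values over six months, some overlap has a probability of at least 82% in every case examined, and about 98% or more at quit rates up to 30% with an eReferral between-clinic SD of 2.5 points. This rests on an assumed quit rate of 10-40%, the fax enrolment figure in both arms, complete follow-up and equal clinic volumes. Incomplete follow-up would lower the counts further.

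What remains to be settled is that the test is not firmly fixed, ignores the randomization strata, and comes with no effect estimate or expected count. This is a modest correction to a secondary analysis.

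**What to change.** - Delete the no-overlap sentence.
- Name one clinic-level test, to be used whatever the overlap: a rank test stratified by health system, either the rank-sum with six:six re-allocation within system or van Elteren's test.
- Report an effect estimate with its interval, for example the arm difference in mean clinic rate with each clinic counted once.
- State the assumed quit rate, the follow-up window and the expected abstainers per clinic.
- If wanted, add the pooled abstainers/smokers permutation test as a sensitivity analysis, noting that it changes the weighting and that its power advantage depends on unequal clinic sizes and the assumed variance.

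The cost is a paragraph of SAP text and a short program. Power falls by at most about 1-2 points if the systems do not differ and rises by several points if they differ substantially. One limit should be stated: six:six re-allocation respects the strata but only approximates the urn procedure, which also balances provider numbers, smoking prevalence and baseline referral rate.

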We would also like to note that the name of one of the health care systems in which the eReferral to the Quitline is being compared to fax-to-quit referral to the Quitline has changed due to a merger. The system formerly known as Wheaton Franciscan is now called Ascension Wisconsin. This change has been noted throughout this document.

Finally, we would like to add two survey items to the post-eReferral survey completed by clinic staff at the end of the Quitline eReferral study (see Appendix A) to assess how healthcare providers are introducing the eReferral to patients. We have found considerable heterogeneity across providers and clinics in response to eReferral and we want to assess whether there is similar heterogeneity in the ways providers report introducing the Quitline and link this to rates of eReferral and Quitline service engagement across clinics (not specific providers) in our analyses of Quitline referral methods

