**Table 2. Intervention Activities and Outcomes**

Intervention	Activities	Key Outcomes
Fax Referral – Fax to Quit Condition (12 clinics)	✓ On site Baseline training (30 minutes) for all clinical staff describing the Wisconsin Tobacco Quitline (WTQL) and its services, which tobacco users are appropriate for a WTQL referral, and workflow for use of that clinic's condition-	✓ Monthly total of adult patient visits to the clinic as well as number and proportion of those adults who report on that clinic visit that they are current tobacco users
eReferral Condition (12 clinics)		
NOTE: apart from their different referral mechanisms, the intervention training,		

feedback, and other activities will be identical for the two intervention conditions	
 
✓ specific WTQL referral mechanism (either F2Q or eReferral)
 
✓ One week post-intervention launch meeting with clinic manager and physician champion to assess the launch and program
 
✓ Monthly aggregate reports sent to clinic contact indicating percentage and volume of tobacco user referred by that site; and number of patients referred who engaged in WTQL services
 
✓ Referral refresher trainings at one month
 
	
 
✓ Percentage and number of patients who smoked referred to the WTQL
 
✓ Number of referred patients who engage in tobacco telephone quitline services
 
✓ Baseline and 6 month post-intervention staff satisfaction regarding the WTQL referral
 
✓ 4 month post-quitline registration date quit rate
 

--	---	--

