## **II. Methods to address Secondary Aim 3: To assess clinician and staff satisfaction with the eReferral and paper F2Q systems.**

In addition to our systematic testing of the impact of eReferral relative to F2Q in terms of rates of smokers to the WTQL as well as cessation rates of those enrolling in WTQL services, we will conduct brief pre- and post-electronic questionnaire surveys of all clinic staff regarding their experience with the two methods of referring patients who smoke to the WTQL. The pre-survey will be sent electronically to all staff members during the three-month Preparation Phase and the post-survey will be sent at six months post-initiation of the study in each clinic. Staff to be surveyed include the Medical Assistants, nurses, clinic manager, and provider staff (physicians, nurse practitioners, and physician assistants). The surveys will be designated by clinical role and will not be further identified. The survey will be designed to target constructs (both "facilitators of" and "obstacles to" adoption of EHR and workflow enhancements) that are implicated by prior research on adoption and maintenance of system changes:

- Task/job training and understanding
- Personal attitudes about smoking
- Appropriateness of activity for role
- Perceived importance to patient and to clinic
- Self-efficacy for task
- Feeling of team membership

Finally, open-ended items on the survey will help ensure that information is gathered on unanticipated or unusual issues that affect referring patients to the Wisconsin Tobacco Quit Line. These surveys are similar to those used extensively in our earlier research on smoking intervention in clinic settings. They were designed to meet high standards with regards to item writing and psychometrics (e.g., Devellis, 2012). The survey to be used for this pre- and post-survey is provided as Appendix A.

2/28/2017 Amendment. The staff survey developed for eReferral to the Quitline has been adapted slightly to assess familiarity with and beliefs about text support programs prior to and after eReferral launch and to assess use of and attitudes toward SmokefreeTXT at the end of the eReferral evaluation period in each clinic. The adapted version of the staff survey is shown in Appendix B. Items I-X and XIX-XX are identical to those used in the existing protocol for Quitline referral. Items XI-XVIII, XXI, and XXIIC

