**Staff Survey Analysis.** Most items on the survey are Likert scale items so their scoring and synthesis will be straightforward. We will compute standard psychometric indices such as item means, variance/standard deviation, and range. We will not subject items to factor analyses or determine coefficient alpha since the items were not designed to index latent dimensions. However, reliability/generalizability analyses will be conducted to determine if level of endorsement varies with type of staff member (this will be done across clinics, within each experimental condition). In formal analyses, we will use GEE (see above) to perform item-specific analyses since respondents will be nested within clinics. Thus, clinic will be treated as a Level 2 variable while staff member will be treated as a Level 1 unit. Because surveys will not carry personal identifiers we will conduct separate analyses on baseline and post-intervention data. The main analyses will test for differences in post-intervention endorsement levels as a function of experimental condition. In a subanalysis we will separately analyze data from the MA's, the only staff group large enough to permit dedicated analysis. These analyses will be repeated for the baseline data. Open ended items will be nonquantitatively synthesized and common or significant themes will be extracted and used to guide interpretation of the survey data.

2/28/2017 Amendment. As in the existing quit line eReferral protocol, staff survey analyses will focus on item means, variance/standard deviation, and range prior to and six months after the SmokefreeTXT eReferral launch. Given that only 1-3 clinics will be involved in the SmokefreeTXT eReferral pilot, however, we will not treat data as nested in clinic and will not examine results by staff role within clinics, and the numbers of particular staff types will be too low to support such an analysis. Survey data will be assessed and coded in the same way in the existing protocol and the SmokefreeTXT pilot.

Figure 1. Manual Fax to Quit: Clinic, Patient, and Data Workflow

[figure not shown]

Figure 2. Fax to Quit Consent Form Used in Clinics

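### The staff-survey comparison sets the baseline survey aside because replies are anonymous, but the clinic's baseline item mean can be used without identifying anyone: a cheap improvement to a secondary analysis

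*Combined protocol and SAP*

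**What the plan says.** Secondary Aim 3 is to assess how satisfied clinicians and staff are with the two referral systems. Table 2 lists as a key outcome "Baseline and 6 month post-intervention staff satisfaction regarding the WTQL referral". On timing, section II (methods for Secondary Aim 3) says: "The pre-survey will be sent electronically to all staff members during the three-month Preparation Phase and the post-survey will be sent at six months". In Appendix A, items I to XV carry no restriction to one time point, so both surveys ask them.

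The analysis is in the Staff Survey Analysis paragraph. It plans item-by-item GEE with staff nested in clinics: "Thus, clinic will be treated as a Level 2 variable while staff member will be treated as a Level 1 unit". It then says: "Because surveys will not carry personal identifiers we will conduct separate analyses on baseline and post-intervention data". The main test is set as follows: "The main analyses will test for differences in post-intervention endorsement levels as a function of experimental condition". The baseline data get a parallel run ("These analyses will be repeated for the baseline data"), but no baseline term enters the post-intervention model.

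Two statements bear on whether a reply can be traced to its clinic. Section II says: "The surveys will be designated by clinical role and will not be further identified". The project summary of the 2/28/2017 amendment, on the two items added to the post survey, plans to "link this to rates of eReferral and Quitline service engagement across clinics (not specific providers").

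**The concern.** The stated reason does not lead to the stated choice. Without personal identifiers, one person's two replies cannot be paired. But clinics were randomised, not persons, and for every item asked twice each clinic has a baseline mean. That mean needs only the clinic to be known, and the planned GEE needs that already.

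The plan uses this device elsewhere. In the Analytic Plan for the Intervention Phase, each clinic's baseline referral rate is a covariate in the primary model. No reason other than anonymity is given for leaving it out of the survey analysis.

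At stake is precision. With 12 clinics per arm, clinics that differ at the start in culture or in satisfaction with the EHR will by chance fall unevenly between arms. The urn randomisation balances number of providers, smoking prevalence and baseline fax-referral rate, but not survey responses. A separate baseline analysis would show an imbalance without removing it from the post-intervention contrast.

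**Working it through.** The documents give no sample size, SD, ICC or power for the survey, so there is no figure of the plan's own to reproduce. The one power statement concerns referral rates.

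**Inputs**
- From the documents: 12 clinics per arm, 24 in total (Clinic Randomization).
- Assumed: ICC 0.05 to 0.15; m = 10 to 20 respondents per clinic; stability of the true clinic effect between surveys 0.6 to 0.8; different staff answering, or no within-person correlation.

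**Formulas**
- Reliability of a clinic mean: R = m × ICC / (1 + (m − 1) × ICC).
- Baseline-to-post correlation of clinic means: r = R × stability.
- Variance of the adjusted contrast relative to post-only: (1 − r²) × (1 + 1/(24 − 4)) = (1 − r²) × 1.05. The factor 1.05 is the cost of estimating one covariate slope with 24 clinics.

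**Results**
- Low (ICC 0.05, m 10, stability 0.6): R = 0.5/1.45 = 0.345; r = 0.207; ratio = 0.957 × 1.05 = 1.005. No gain.
- Middle (ICC 0.10, m 20, stability 0.8): R = 2/2.9 = 0.690; r = 0.552; ratio = 0.696 × 1.05 = 0.730. Variance 27% lower.
- High (ICC 0.15, m 20, stability 0.8): R = 3/3.85 = 0.779; r = 0.623; ratio = 0.611 × 1.05 = 0.642. Variance 36% lower.
- Break-even: 1 − r² = 1/1.05, so r² = 0.0476 and r = 0.22.

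**Middle case in practical terms.** In item-SD units the variance of a clinic mean is 0.10 + 0.90/20 = 0.145. The standard error of the arm difference is √(2 × 0.145/12) = 0.16, which is also the SD of the chance baseline difference. The difference detectable with 80% power at two-sided 0.05 falls from 0.46 to 0.39 item SD (noncentral t, 22 and 21 df). Among simulated trials with no true effect and a baseline difference above one standard error, the post-only contrast is off by 0.13 item SD on average; after adjustment it is off by 0.00.

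**Wider assumptions.** Take m 10 to 30, ICC 0.02 to 0.20, stability 0.5 to 0.8, and a within-person correlation of 0 to 0.5 if the same staff answer both times. The ratio then runs from 0.44 to 1.04. Simulation (40,000 trials per scenario) agrees: 0.72 against 0.73 in the middle case, and 1.04 in the worst.

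**A model that should not be swapped in.** An unconstrained condition-by-period model on stacked data estimates the difference in change. Its variance relative to post-only is 2(1 − r): 1.59 at r = 0.207, 0.90 at r = 0.552 and 0.75 at r = 0.623. It exceeds 1 whenever r is below 0.5.

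**The case against.** The strongest reply is that the planned test is valid as it stands. It compares randomised arms after intervention with clustering by clinic, and chance imbalance is already part of its standard error. That stands. A reader might infer that the post-only contrast is biased; the design does not support this, because randomisation makes it unbiased on average.

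A reader might also infer that the plan means to judge change by setting a baseline p-value beside a post-intervention one. It does not say so: it names one main contrast and repeats it at baseline. Nor does Secondary Aim 3 ask whether satisfaction changed more in one arm. The stated interaction between condition and period belongs to the hypotheses on referrals and contacts, and a post-intervention comparison does answer the survey aim.

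The gain is also uncertain. All the survey parameters are assumed, clinics may have as few as three providers, and break-even lies inside the assumed range. Items XIII to XV of Appendix A rate the referral method and its feedback. Only some of the systems' clinics offered fax referral beforehand, and in the eReferral arm the rated method then changes, so baseline may predict these items poorly. This also stands, and it rules out an unconditional claim that precision is lost.

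Finally, section II says surveys are marked by role only, and Appendix A has no clinic item. This is a conflict within the plan, but the clinic-nested GEE needs the clinic just as much as the adjustment does.

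**Conclusion.** The point holds as a likely gain in efficiency and a correction for chance imbalance in a secondary analysis. Anonymity does not justify leaving out the clinic's baseline mean. Under the stated assumptions the variance of the arm contrast changes by about 0% to -36%. It could rise slightly if the correlation of clinic means is well below 0.22, and it could fall further if largely the same staff answer both surveys. The documents do not allow a narrower range. The primary referral outcome is not affected. This is a cheap improvement, not a flaw that invalidates the survey result.

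**What to change.** In Staff Survey Analysis, replace the sentence on separate analyses with wording such as: *For each item asked at both surveys, the post-intervention GEE will include condition and the clinic's baseline mean for that item, with clinic as the cluster. The contrast without the baseline term will be reported as a sensitivity analysis.* Do not use an unconstrained condition-by-period model in its place.

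State that each survey records a clinic code and no personal identifier, and reconcile section II with the clinic-nested GEE on this. The planned analysis needs the code in any case.

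The cost is a change of wording and one clinic-level degree of freedom (22 to 21), with variance up by at most about 4% over the ranges examined if the correlation is very low. The baseline survey is already planned, so nothing is collected beyond the clinic code.
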